12.3 Early Stopping Guidelines

In the event 2 DLTs occur for more than 1 subject at a NOTS (number of tumor sites) level (as defined in [section 7.2](#)), study enrollment will be immediately halted. There will be at least 14 days following completion of the FUS treatment of the patient(s) on study before any subsequent patient is enrolled. After re-evaluation and consultation with the HICCC DSMC board, the trial may re-initiate enrollment with adjusted treatment parameters after a consensus is agreed upon by the Sponsor-Investigator and the HICCC DSMC, and a subsequent modification is reviewed/approved by the local PRMC/IRB. If a consensus cannot be reached, no further enrollment will be permitted on the trial and closure procedures will be initiated. In addition, the study will be discontinued at any given time if more than 20% of patients experiencing medical complications including the development of significant, irreversible deterioration during the treatment. With this rule and under the assumption of the true probability of having the medical complication is 10%, the probability of stopping the study due to the medical complication is 0.02 when the targeted total sample size is 6 and is 0.053 when the targeted total sample size is 9.

If the MRI to confirm opening of the BBB for any subject is irregular at any time during the cycles, the subject will not receive the scheduled dose treatment until a decision is made by the investigating team.

If the MRI confirm the closure of the BBB for any subject are irregular at any time, the subject will not receive any further FUS treatments and will receive another MRI to confirm closure every 48 hours for a maximum of 3 times. If the subject does not show BBB closure after 3 MRIs, the subject will come off the study. The subject will be able to receive the scheduled dose of drug, unless otherwise specified by the investigating team.

Response and progression will be evaluated in this study using the international criteria proposed by the updated Pediatric Response Assessment in Neuro-oncology (RANO) guidelines[49].

| Criterion | Complete Response | Partial Response | Stable Disease | Progressive Disease |
|----------------------------------------|---------------------|---------------------|---------------------------------|---------------------|
| T1-weighted post-Gd measurable disease | None | ≥50% decrease | <50% decrease but <25% increase | ≥25% increase |
| T2/FLAIR | Stable or decreased | Stable or decreased | Stable or decreased | Increased |
| New lesion | None | None | None | Present |
| Corticosteroids | None | Stable or decreased | Stable or decreased | NA |
| Clinical status | Stable or increased | Stable or increased | Stable or increased | Decreased |
| Requirement for response | All | All | All | Any |

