7.2 Trial Design

The trial will follow a 3+3 “NOTS” or Number of Tumor Sites escalation scheme. The “number of tumor sites” in reference to here in the number of openings in the blood brain barrier using Focused Ultrasound (FUS). Subjects will start the first cycle of the treatment arm with 1 tumor site and move on to incrementing NOTS levels as depicted in Figure 3, if no dose limiting toxicities

(DLTs) are observed (we use the term Dose Limiting Toxicity where dose = Number of Tumor Sites (NOTS)):

- 1 tumor site (level "NOTS Level A"),
- 2 tumor sites (level "NOTS Level B") or
- 3 tumor sites (level "NOTS Level C")

For a detailed description of DLTs please refer to [Section 12.2](#).

[figure not shown]

Figure 3: NOTS (Number of tumor Sites) Escalation Schema

For each subject the following FUS NOTS escalation scheme will be followed:

- Each subject will start off with receiving FUS treatment in 1 tumor site (NOTS Level A) for Cycles 1 and 2.
- If 0 DLTs are noted during pre-cycle 3 follow-ups and MRI (without contrast), the subject will receive FUS treatment at 2 tumor sites (NOTS Level B) in the 3rd cycle.
 - If 1 DLT is noted during pre-cycle 3 follow-ups and MRI (without contrast), the subject will discontinue treatments and will come off the study (please refer to [Section 12.3](#) for Early Stopping Guidelines). Other subjects may continue to enroll.
 - If 2 DLTs are noted at the same NOTS level, enrollment will be halted following Early Stopping Guidelines detailed in [Section 12.3](#).
- If 0 DLTs are noted during pre-cycle 4 MRI (without contrast) and follow-up, the subject will continue to receive FUS treatment at 2 tumor sites (NOTS Level B) in the 4th cycle.
 - If 1 DLT is noted during pre-cycle 4 follow-ups and MRI (without contrast), the subject will discontinue treatments and will come off the study (please refer to [Section 12.3](#) for Early Stopping Guidelines).

refer to [section 12.3](#) for Early Stopping Guidelines). Other subjects may continue to enroll.

- If 2 DLTs are noted at the same NOTS level, enrollment will be halted following Early Stopping Guidelines detailed in [Section 12.3](#).
- If 0 DLTs are noted during pre-cycle 5 MRI (without contrast) and follow-up, the subject will receive the next escalated FUS treatment at 3 tumor sites (NOTS Level C) in the 5th cycle.

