 - If 1 DLT is noted during pre-cycle 5 follow-ups and MRI (without contrast), the subject will discontinue treatments and will come off the study (please refer to [section 12.3](#) for Early Stopping Guidelines). Other subjects may continue to enroll.
 - If 2 DLTs are noted at the same NOTS level, enrollment will be halted following Early Stopping Guidelines detailed in [Section 12.3](#).
- If 0 DLTs are noted during pre-cycle 6 MRI (without contrast) and follow-up, the subject will continue to receive FUS treatment at 3 tumor sites (NOTS Level C) in the 6th cycle.
 - If 1 DLT is noted during pre-cycle 6 follow-ups and MRI (without contrast), the subject will discontinue treatments and will come off the study (please refer to [section 12.3](#) for Early Stopping Guidelines). Other subjects may continue to enroll.
 - If 2 DLTs are noted at the same NOTS level, enrollment will be halted following Early Stopping Guidelines detailed in [Section 12.3](#).

Within each cycle, if 1 DLT is noted the subject will discontinue treatments and will come off the study (please refer to [section 12.3](#) for Early Stopping Guidelines). Other subjects may continue to enroll.

If 2 DLTs are noted at the same NOTS level for a subject, study enrollment will be halted following Early Stopping Guidelines detailed in [Section 12.3](#).

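### Two DLTs at a NOTS level halt enrolment at once, but no text shown requires a hold on escalation or FUS for DLT-free subjects on treatment while the DSMC review is pending

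*Combined protocol and SAP*

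**What the plan says.** Section 7.2 escalates within the subject: "For each subject the following FUS NOTS escalation scheme will be followed". Everyone has one site in Cycles 1 and 2 (Level A), two in Cycles 3 and 4 (Level B) and three in Cycles 5 and 6 (Level C). A subject with no DLT at a checkpoint continues or moves up. For the last step the text reads "If 0 DLTs are noted during pre-cycle 5 MRI (without contrast) and follow-up, the subject will receive the next escalated FUS treatment at 3" sites. A subject with one DLT stops treatment and leaves the study, while others may still enrol.

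The two-DLT rule appears in three forms:

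- Sections 7.2 and 12.1: "If 2 DLTs are noted at the same NOTS level for a subject, study enrollment will be halted following Early Stopping Guidelines".
- Sections 7.2 and 12.1 also state it for two DLTs at the same level, without saying whose.
- Section 12.3: "In the event 2 DLTs occur for more than 1 subject at a NOTS (number of tumor sites) level", followed by "study enrollment will be immediately halted".

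Section 12.3 continues: "There will be at least 14 days following completion of the FUS treatment of the patient(s) on study before any subsequent patient is enrolled". A review with the DSMC comes next, and enrolment may reopen with changed parameters if the sponsor-investigator and the DSMC agree and a modification is approved. Otherwise the trial closes. A separate rule in 12.3 says "the study will be discontinued at any given time if more than 20% of patients experiencing medical complications".

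**The concern.** A halt to enrolment protects the children who would meet the hazard next only if newcomers enter at the level that caused the trouble. Here they do so only at Level A. If the two DLTs arise at Level B or C, the children nearest the hazard are those already on study: one being treated at that level, or one whose next checkpoint leads into it. For them the text gives a forward instruction at 0 DLTs and no counter-instruction once two other subjects have had DLTs at that level.

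At stake is what site staff should do between the second DLT and the DSMC's decision. Following the text literally, they could treat or escalate a child at a level whose safety is under review. This is a paediatric study that names safety as its primary endpoint (12.4).

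**Working it through.** **1. What each section orders after two DLTs at a level**

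| Section | Immediate action | DLT-free subjects on treatment |
|---|---|---|
| 7.2 | halt enrolment, refer to 12.3 | not mentioned; 0-DLT branch continues or escalates |
| 12.1 | halt enrolment, refer to 12.3 | timing of doses may be changed at PI discretion |
| 12.3 | halt enrolment; then re-evaluation, DSMC consultation, possible closure | no interim hold stated |
| 12.4 | interruption is to be considered if similar toxicities occur in more than one subject | permitted, not required |
| 13.3 | DSMC monitors every treated subject | can act, no automatic hold |

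**2. Whose DLTs govern escalation.** The per-subject wording of 7.2, and the purpose given in 7.5 for the pre-escalation MRI (clearing that subject), point to the subject's own count. Against that, the opening rule of 7.2 has subjects "move on to incrementing NOTS levels as depicted in Figure 3, if no dose limiting toxicities" are observed, without limiting it to their own. Figure 3 may settle this. If it stops escalation study-wide, that half of the gap closes, and the visible text is silent only on FUS at the current level.

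**3. Timing.** Inputs (7.5): six cycles of 2 weeks, 1 week apart, so 21 days from start to start; FUS on Days 1, 3 and 5. Section 7.4 says Week 2 is similar apart from the contrast MRIs, which adds Days 8, 10 and 12.

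- Level B starts on Day 1 + 2×21 = 43; last session 64 + 11 = Day 75.
- Level C starts on Day 1 + 4×21 = 85; last session 106 + 11 = Day 117.
- A newcomer is 42 days from Level B and 84 days from Level C.

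**4. Exposure before a scheduled review.** The DSMC meets twice a month (13.3), so take 14 days.

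- FUS in both weeks: a window starting on cycle Day 1 holds Days 1, 3, 5, 8, 10 and 12, which is 6 sessions. One starting on Day 6 holds Days 8, 10 and 12, which is 3. Range 3 to 6.
- FUS on Days 1, 3 and 5 once per cycle, which 7.5 and the appendices also allow: a window starting on Day 1 holds 3; one starting on Day 6 holds none. Range 0 to 3.

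Section 11.3.4 sends serious adverse events that are not unanticipated problems to the DSMC within 24 hours, so serious DLTs may be seen sooner.

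**5. Overlap.** If the 14-day sentence is a standing stagger, the next full-course subject starts no earlier than Day 117 + 14 = 131, or 130 days later. Fifteen subjects need 14×130 = 1,820 days (about 5.0 years) from first to last start, less if subjects progress early. There would be no overlap and no gap. The sentence sits inside the halt procedure and refers to patient(s), which suggests a wait after a halt. No accrual period is stated, so the 5 years do not decide the reading.

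**6. The 20% rule.** First, the plan's own figures, from the binomial with p = 0.10:

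- n = 6: P(X≥3) = 1 − 0.5314 − 0.3543 − 0.0984 = 0.0159 (printed 0.02). P(X≥2) = 0.1143.
- n = 9: P(X≥3) = 1 − 0.3874 − 0.3874 − 0.1722 = 0.0530 (printed 0.053). P(X≥2) = 0.2252.

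The printed values match three or more events. The literal wording is already met by two (2/6 = 33.3%, 2/9 = 22.2%). If DLTs count as medical complications, which the rule does not say, two affected subjects exceed 20% up to n = 9 but not from n = 10 (20.0%) to n = 15 (13.3%).

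**7. Section 12.6** terminates the investigation for a serious adverse event due to the procedure, which would catch many sonication DLTs. The DLT definition in 12.2 is wider: it includes Grade 3 nervous-system events only possibly attributed to sonication, and systemic drug toxicity.

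**8. The trigger.** A subject leaves at the first DLT, so two DLTs for one subject can hardly occur unless they arise together. Only the across-subject wording in 12.3 is workable.

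**The case against.** The strongest reply is that the plan has several brakes. Section 12.3 goes beyond enrolment, to re-evaluation, changed treatment parameters and possible closure. The PI may alter dose timing (12.1), unresolved Grade 2 or higher toxicity halts that child's treatment (12.1), and the DSMC follows every treated subject (13.3) and receives summaries of toxicity and escalation (13.4). Section 13.3 even discontinues the study for a reaction to therapy, although 13.2 withdraws only the subject for the same event. Each escalation needs the child's own clean follow-up and MRI. In progressive DMG, letting a DLT-free child continue is defensible.

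Much of this stands and limits the weight of the point. None of it is a required hold after two DLTs at a level.

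A reader might infer that the trial would press on with escalation with nothing to stop it, or that children face a measurable excess risk. The documents support neither. Section 12.6 and the 20% rule can end the study, the discretionary provisions allow a pause, and Figure 3 may stop escalation. No DLT rate is given from which to compute a risk. For purely systemic panobinostat DLTs, holding the number of sites may not help, because the dose is 15 mg/m² at every level.

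**Conclusion.** The point holds in a limited form. In the text shown, halting enrolment is the only immediate action after two DLTs at a NOTS level. A hold for DLT-free subjects on treatment is permitted but not required.

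The gap rests on three assumptions:

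- subjects overlap on treatment, so the 14-day sentence is not a standing stagger;
- the DLTs trigger neither 12.6 nor the 20% rule;
- Figure 3 does not already stop escalation.

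Under these, a mid-course subject could receive 3 to 6 further FUS sessions in 14 days (0 to 3 on the once-per-cycle reading), or escalate, before a scheduled DSMC meeting. At Levels B and C the enrolment halt does not reach those subjects. At Level A it does cut exposure, since newcomers start there. Confidence is medium because the figure is unseen. It should be fixed because the remedy is cheap, not because a harm has been shown.

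**What to change.** Amend 7.2, 12.1 and 12.3 as follows.

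- Two DLTs at a NOTS level, counted across subjects, halt enrolment and also suspend, for all on-study subjects until the DSMC review, escalation into that level or above and FUS at that level or above.
- A subject may continue at a lower level already cleared if the investigator and the DSMC agree.
- Where the DLTs are at Level A, or are purely systemic panobinostat toxicity, the DSMC decides on FUS and drug.
- Replace the single-subject trigger in 7.2 and 12.1 with the across-subject count.
- State whether the 14-day interval is a standing stagger or applies only after a halt.

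This is a wording change that uses the review already in 12.3. The cost is a treatment delay for a few subjects: about 2 weeks if settled at the next DSMC meeting, longer if a PRMC/IRB modification is needed. That delay matters in progressive DMG, which is why continuation at a cleared lower level is allowed.

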7.5 Treatment MRIs

Treatment MRI breakdown:

- 1 cycle of Panobinostat= 2 weeks of 3 alternate treatment days. Subjects will undergo 6 cycles, each spaced 1 week apart.
- In each cycle, subjects will receive Focused Ultrasound (NgFUS) and injection of DEFINITY® microbubbles using NgFUS system in the Radiation Oncology Suite on Days 1, 3, and 5 (all treatment days).
- **MRI to Determine Opening of Blood Brain Barrier:** On Week 1 Day 1 of each cycle, 2-4 hours post FUS treatment with DEFINITY® microbubbles on Day 1, subjects will receive an MRI with injection of Gadolinium contrast.
- Treatment includes receiving Oral Panobinostat at 15 mg/m² on the days of NgFUS treatment.
- **MRI to Confirm Closure of Blood Brain Barrier:** On Week 1 Day 3 of every other cycle (Cycles 1, 3 and 5), subjects will undergo MRI with gadolinium pre Day 3 FUS treatment to ensure closure of the blood brain barrier. This MRI will be conducted within 24-48 hours of the completion of the Day 1 FUS treatment.
- A number of tumor sites (NOTS) escalation scheme for the number of tumor sites targeted by FUS will be followed as laid out in [section 7.2](#). As stated in the section, an MRI (without contrast) will be performed prior to each escalation to clear the subject of any possible DLTs and increase in tumor size.

Subjects will receive FUS treatment in the Radiation Oncology Suite and drug treatments in either the Outpatient Clinic on HIP-7 or in Radiation Oncology immediately after the FUS treatment. Subjects will be monitored by the study team with Neurological Exams on treatment days, as determined necessary. Subjects will not be kept as inpatients for treatment days and will be discharged following completion of treatment day, unless deemed necessary by the study team.

See [Appendix A](#) and [B](#) on pages 47 and 49 respectively for a detailed breakdown of visits and data collected.

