10.1 Sample Size Determination

A minimum of 3 and maximum of 15 patients will be recruited in the study. The minimum number of subjects is to account for “dose” limiting toxicities disallowing more subjects to be enrolled. As this is a feasibility study, the power and sample size is not justified. However, successful methodology will be concluded if the BBB opening is safely opened in at least 75% of the cases as evidenced on MRI. The scan with the BBB opening will be compared to the scan before BBB opening for each patient. Power analysis shows that for a detectable difference of 72 mm^3 (after BBB opening - before BBB opening) and a standard deviation of 50 mm^3 , at least 6 subjects are needed to report a result at the level of $\alpha=0.05$ and Power=0.80 with paired student's t-test.

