11. ADVERSE EVENT REPORTING

11.1 Definitions

Adverse Event

An adverse event (AE) is any untoward or unfavorable medical occurrence in a human subject, including abnormal sign, symptom or disease associated with the subject's participation in research, whether or not considered related to the subject's participation in the research. For the treatment period and 30 days post, all adverse events (AEs) according to the Common Terminology Criteria for Adverse Events (CTCAE) version 5.0 will be captured. Baseline abnormalities or pre-existing conditions will be identified and recorded as part of the pre-treatment work-up. Pre-existing conditions will not be subsequently reported as adverse events unless the severity increases after the start of treatment, or unless the pre-existing condition resolves and then recurs during treatment. After day 30 of follow-up, only grades 3, 4, and 5 AEs will be captured through 90 days following the neurosurgical procedure. All recorded AEs must have their attribution to the study procedures recorded, as well as their onset and resolution date (if known).

Serious Adverse Event

A serious adverse event (SAE) is any AE that is:

- fatal
- life-threatening
- requiring inpatient hospitalization/prolongation of existing hospitalization, unless:
 - routine treatment or monitoring of the studied indication, not associated with any deterioration in condition (procedures such as central line placements, paracentesis, pain control)
 - elective or pre-planned treatment for a pre-existing condition that is unrelated to the indication under study and has not worsened since the start of study the drug
 - social reasons and respite care in the absence of any deterioration in the subject's general condition
- resulting in persistent or significant disability or incapacity
- a congenital anomaly or birth defect
- an important medical event

Important medical events are those that may not be immediately life threatening but are clearly of major clinical significance. They may jeopardize the subject and may require intervention to prevent one of the other serious outcomes noted above.

Any adverse event that results in hospitalization or prolonged hospitalization should be documented and reported as a serious adverse event unless the AE meets one of the criteria listed below:

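### The stopping probabilities printed in section 12.3 (0.02 at 6 subjects, 0.053 at 9) belong to a 3-event trigger, but more than 20% of 6 or 9 is reached at 2 events

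*Combined protocol and SAP*

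**What the plan says.** Section 12.3 (Early Stopping Guidelines) contains a mandatory rule for the whole study: "the study will be discontinued at any given time if more than 20% of patients experiencing medical complications". The events are described as "medical complications including the development of significant, irreversible deterioration during the treatment".

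The next sentence evaluates that same rule, assuming a true complication probability of 10%. It states that "the probability of stopping the study due to the medical complication is 0.02 when the targeted total sample size is 6", and that the probability "is 0.053 when the targeted total sample size is 9".

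Section 10.1 gives the recruitment range: "A minimum of 3 and maximum of 15 patients will be recruited in the study". Section 12.3 prints no stopping probability for 15. It does not say whether the 20% refers to patients treated so far, to the targeted total or to the maximum, and it sets no minimum number of patients or events.

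**The concern.** A false-stop probability tells the investigators, the DSMC and the IRB how often a safety rule would close a study whose complication rate is acceptable. It is useful only if it describes the rule as written. Here the written threshold and the printed probabilities imply different event counts.

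A monitor who applies the wording to 6 or 9 subjects would stop at two complications. A monitor who works back from the printed probabilities would stop at three. In a paediatric trial of at most 15 subjects, that one-event difference decides whether the study continues.

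The qualifying event is only partly specified. Section 12.3 gives an example (significant, irreversible deterioration) and a period (during treatment), but no grade and no attribution. Section 12.2, by contrast, gives grade, treatment-relatedness and a window for DLTs. The subjects have progressive DMG, and section 2.1 cites a median survival of about 9 months from diagnosis for the pontine form. Deterioration from disease during treatment is therefore foreseeable, and 12.3 does not say whether it counts.

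**Working it through.** **Inputs.** From 12.3: threshold strictly above 20%, true rate p = 0.10, targeted totals 6 and 9, printed results 0.02 and 0.053. From 10.1: maximum 15. Subjects are taken as independent and fully observed, and the 12.3 rule is considered alone.

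**Step 1: reproduce the printed figures.** With X binomial(n, 0.10):

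- n = 6: P(X ≥ 3) = 1 − 0.9⁶ − 6(0.1)(0.9⁵) − 15(0.1²)(0.9⁴) = 1 − 0.5314 − 0.3543 − 0.0984 = 0.0159, which rounds to 0.02.
- n = 9: P(X ≥ 3) = 1 − 0.9⁹ − 9(0.1)(0.9⁸) − 36(0.1²)(0.9⁷) = 1 − 0.3874 − 0.3874 − 0.1722 = 0.0530.

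Both match, so the printed figures are correct for a trigger of 3 events.

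**Step 2: apply the written threshold to the same totals.** 1/6 = 17% and 1/9 = 11% do not exceed 20%. 2/6 = 33% and 2/9 = 22% do. The trigger is 2 events at both sizes.

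- n = 6: P(X ≥ 2) = 1 − 0.5314 − 0.3543 = 0.114.
- n = 9: P(X ≥ 2) = 1 − 0.3874 − 0.3874 = 0.225.

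The ratios are 0.1143/0.0159 = 7.2 (5.7 against the rounded 0.02) and 0.2252/0.0530 = 4.2. Checking continuously does not change these values, because a fixed count, once reached, stays reached.

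**Step 3: look for a percentage rule that gives 3 events.** Requiring 3 events under a rule of the form above t needs 2/6 ≤ t < 3/6 at n = 6 and 2/9 ≤ t < 3/9 at n = 9. No t satisfies both. With t = 20%, 3 is the first count above the threshold only for denominators 10 to 14, none of which is named as a sample size. At the named maximum of 15, 3/15 is exactly 20%. A rule of at least 20% of 15 would therefore need 3 events and would reproduce both printed figures. The written rule, more than 20% of 15, needs 4.

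**Step 4: a running denominator.** The rule applies at any time, so it could be read against subjects observed so far. One event among the first four subjects then stops the study; from subject 5 to 9 it takes two.

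- By 4: 1 − 0.9⁴ = 0.3439.
- By 6: 0.3439 + 0.6561 × 0.1² = 0.350.
- By 9: 0.3439 + 0.6561 × P(X ≥ 2 | n = 5) = 0.3439 + 0.6561 × 0.0815 = 0.397.

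These are upper values: they assume that each subject is fully observed before the next enters the denominator.

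**Stopping probability at a true 10% rate**

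| Reading | by 6 | by 9 |
|---|---|---|
| Printed in 12.3 | 0.02 | 0.053 |
| 3 events (unstated) | 0.016 | 0.053 |
| More than 20% of targeted total (2 events) | 0.114 | 0.225 |
| More than 20% of 15 (4 events) | 0.0013 | 0.0083 |
| More than 20% of subjects so far (upper value) | 0.350 | 0.397 |

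**Step 5: values up to 15 for the two likely intentions.**

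- *3 events:* P(X ≥ 3 | n = 15) = 0.184.
- *At least 2 events and more than 20% of those treated:* 2 events through subject 9, 3 at subjects 10 to 14, 4 at 15. By subject 9 this is 0.2252. Subjects 10 to 14 add 0.3874 × P(X ≥ 2 | n = 5) + 0.3874 × P(X ≥ 3 | n = 5) = 0.3874 × 0.0815 + 0.3874 × 0.0086 = 0.0349. Subject 15 adds nothing, because anyone still continuing has at most 2 events by subject 14. The total is 0.260.

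**Step 6: protection at a true 30% rate, by subject 6.** P(X ≥ 2) = 1 − 0.1176 − 0.3025 = 0.580. P(X ≥ 3) = 0.5798 − 0.3241 = 0.256.

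**The case against.** The best defence is that the numbers are sound and one phrase is loose. If the authors meant at least 20% of the maximum of 15, the trigger is 3 events and both printed probabilities follow exactly. That is a plausible origin and points to an easy repair. It remains an inference: 12.3 does not mention 15, and its wording excludes the case of exactly 20%. Applied literally to 15, the rule would stop less often than printed.

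A second defence is that other provisions act first on many of these events. Section 12.6 terminates the investigation for a serious adverse event due to the procedure, and the serious category in 11.1 includes events "resulting in persistent or significant disability or incapacity". Section 13.3 discontinues the study for a reaction to the therapy, two DLTs halt enrollment under 12.3, and 12.4 considers interruption for similar toxicities in more than one subject. This stands as a limit on practical impact. It does not rescue the printed probabilities, which are presented as properties of the 20% rule itself.

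A reader might also infer that one complication among the first four subjects closes the study, with a chance of about one in three at an acceptable rate. The documents do not establish this. The running denominator is possible, but the sentence that evaluates the rule refers to a targeted total sample size, and the running values are the furthest above the printed ones. They also assume no overlap between subjects, and the accrual pattern is not stated. Nor is it right that the event is wholly undefined: an example and a period are given.

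**Conclusion.** The point holds as a mismatch between a written safety rule and the probabilities attached to it. Measured against the targeted totals that 12.3 itself uses, the false-stop probability at a 10% rate is 0.114 rather than 0.02 at 6 subjects, and 0.225 rather than 0.053 at 9. Because no denominator or minimum count is stated, other readings remain open, ranging from 0.0013 to 0.350 at 6 and from 0.0083 to 0.397 at 9.

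The figures rest on independent, fully observed subjects and on the 12.3 rule operating alone. It would go too far to conclude that the trial will stop too often. The direction of the error depends on the denominator, and the documents do not give the share of complications that 12.6 or 13.3 would catch first, so the net effect cannot be calculated. The arithmetic is certain; which trigger was intended is not.

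**What to change.** Amend 12.3 to state the rule as event counts by number treated, name the denominator, and replace the two printed probabilities with matching ones up to the maximum of 15. The sponsor and the DSMC should choose the trigger:

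- **If 3 events was intended:** write 3 or more patients (at least 20% of 15). Keep 0.016 and 0.053 for 6 and 9, and add 0.184 for 15.
- **If more than 20% of those treated, with at least 2 events, was intended:** write 2 events through subject 9, 3 at subjects 10 to 14 and 4 at 15. Print 0.114, 0.225 and 0.260 by subjects 6, 9 and 15.

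Under either choice, state the grade and attribution of a qualifying complication, and whether deterioration due to the tumor counts.

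The cost is a short amendment, with no added patients or procedures. The 2-event version carries a less favourable printed false-stop figure. The 3-event version reacts more slowly to a harmful treatment: at a true 30% rate it stops by subject 6 with probability 0.256, against 0.580 for the 2-event version.
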